8.3.10 IMP Injection Site Reactions

Any reactions at the IMP injection site(s) (ie, ISRs) will be collected as AEs and detailed information regarding symptoms etc, will be collected on a specific CRF.

8.4 Overdose

For this study, any dose of AZD8233 greater than the planned dose will be considered an overdose.

- An overdose with associated AEs is recorded as the AE diagnosis/symptoms on the relevant AE modules in the eCRF and on the Overdose eCRF module
- An overdose without associated symptoms is only reported on the Overdose eCRF module

If an overdose on an AstraZeneca study intervention occurs in the course of the study, the investigator or other site personnel inform appropriate AstraZeneca representatives immediately, but **no later than 24 hours** of when he or she becomes aware of it.

The designated AstraZeneca representative works with the investigator to ensure that all relevant information is provided to the AstraZeneca Patient Safety data entry site **within one or 5 calendar days** for overdoses associated with an SAE (see section 8.3.7) and **within 30 days** for all other overdoses.

8.5 Human Biological Samples

Instructions for the collection and handling of biological samples will be provided in the study specific laboratory manual. Samples should be stored in a secure storage space with adequate measures to protect confidentiality. For further details on Handling of Human Biological Samples see [Appendix C](#).

Samples will be stored for a maximum of 15 years from the date of the issue of the CSR in line with consent and local requirements, after which they will be destroyed/repatriated.

- PK samples (assessing AZD8233 total full length ASOs) will be disposed of after Bioanalytical Report finalization or 6 months after issuance of the draft Bioanalytical Report (whichever is earlier), unless consent is obtained for future analyses.
 - PK samples may be disposed of or anonymised by pooling. Additional analyses may be conducted on the anonymised, pooled pharmacokinetic samples to further evaluate and validate the analytical method. Any results from such analyses may be reported separately from the Clinical Study Report (CSR).

- Remaining ADA sample aliquots will be retained at AstraZeneca or its designee for a maximum of 15 years following issue of the CSR. Additional use includes but is not limited to further characterization of any ADAs, confirmation and/or requalification of the assay as well as additional assay development work. The results from future analysis will not be reported in the CSR.

8.5.1 Pharmacokinetics

Plasma samples will be collected for measurement of concentration of AZD8233 (total full length ASOs) as specified in the SoA.

Samples may be collected at additional time points during the study if warranted and agreed upon between the investigator and the sponsor, eg, for safety reasons. The timing of sampling may be altered during the course of the study based on newly available data (eg, to obtain data closer to the time of peak or trough matrix concentrations) to ensure appropriate monitoring.

Plasma samples will be used to analyse the PK of AZD8233. The samples collected may also be used to evaluate safety or efficacy aspects related to concerns arising during or after the study.

Samples will be collected, labelled, stored, and shipped as detailed in the Laboratory Manual.

8.5.1.1 Determination of Drug Concentration

Samples for determination of drug concentration (AZD8233 total full length ASOs) in plasma will be assayed at bioanalytical test sites operated by or on behalf of AstraZeneca, using an appropriately validated bioanalytical method. Full details of the analytical method used will be described in a separate bioanalytical report.

Placebo samples will not be analysed, unless there is a need to confirm that correct treatment has been given to study participants.

Drug concentration information that would unblind the study will not be reported to investigative sites or blinded personnel until the study has been unblinded.

Incurred sample reproducibility analysis or additional assay development/validation work, if any, will be performed alongside the bioanalysis of the test samples. The results from the evaluation, if performed, will be reported in a separate Bioanalytical Report.

8.5.2 Immunogenicity Assessments

Blood samples for immunogenicity assessments (ADA) in plasma will be collected according to the SoA (Table 1).

The presence or absence of ADAs will be determined in the plasma samples using a validated bioanalytical method. A tiered testing scheme will be employed, with the first step being screening. Samples found positive in the screening step will be tested in the confirmatory

step. Samples confirmed positive for ADA in the confirmatory step will undergo endpoint titre determination. Full details of the analytical method and analyses performed will be described in a separate bioanalytical report.

ADA samples may also be further tested for characterisation of the ADA response. Study results may be reported independently to ADA follow-up.

Samples will be collected, labelled, stored, and shipped as detailed in the Laboratory Manual.

Participants with treatment-emerging ADA-positive titres at the last study visit, and that has a titer of at least 800 that is > 2 dilution steps higher than at baseline, may be asked to return to provide another sample in the time frame approximately 3-6 months after the last study visit.

8.5.3 Pharmacodynamics

8.5.3.1 Collection of Samples

Blood samples will be collected for measurement of LDL-C and other lipids, which will be measured in serum using a validated analytical method. Plasma PCSK9 levels will be measured using a validated analytical method.

Pharmacodynamic laboratory assessments include:

- LDL-C
- PCSK9
- Triglycerides
- Lipoprotein profile (particle size and number)
- Biomarker analyses

And other lipid parameters:

- Total cholesterol
- HDL-C
- Non-HDL-C (Calculated)
- VLDL-C
- Remnants cholesterol (calculated)
- Apo B
- Apo A1
- Lp(a)
- LDL-C/Apo B

For storage, re-use and destruction of pharmacodynamic samples see Section 8.5 and [Appendix C](#).

8.6 Human Biological Sample Biomarkers

8.6.1 Collection of mandatory samples for biomarker analysis

By consenting to take part in the study, the participant consents to take part in the mandatory research components of the study.

- Samples for biomarker research are required and will be collected from all participants in this study as specified in the SoA (Table 1).
- CCI [REDACTED]
- Biomarkers to be taken:
 - Blood (for plasma and serum) and urine sample analyses
 - Plasma and/or urine samples will be collected for targeted and unbiased -omics approaches, PD biomarkers and biomarker research relative to safety, tolerability and PK profiles, to evaluate their association with the observed clinical responses to AZD8233 treatment.

8.7

CCI [REDACTED]

CCI [REDACTED]

CCI [REDACTED]

CCI [REDACTED]

CCI [REDACTED]

8.8 Health Economics

Health Economics/Medical Resource Utilization and Health Economics parameters are not evaluated in this study.

9 Statistical Considerations

9.1 Statistical Hypotheses

The formal hypotheses tests will focus on the treatment effect of AZD8233 versus placebo on the efficacy endpoints related to LDL-C and PCSK9 (Table 6). To maintain a family-wise

Type I error rate of 5%, the hypotheses will be evaluated in a hierarchical sequence by a two-sided test at a 5% significance level until a test fails to reject the null hypothesis or until all the listed null hypotheses are rejected. Any subsequent test will be considered exploratory. Statistical tests will be done in the order as listed in Table 6.

Table 6 Hierarchical Order for Statistical Testing

Order	Null hypothesis	Alternative hypothesis
1	$\mu(\text{LDL-C, A}) = \mu(\text{LDL-C, P})$	$\mu(\text{LDL-C, A}) \neq \mu(\text{LDL-C, P})$
2	$\mu(\text{PCSK9, A}) = \mu(\text{PCSK9, P})$	$\mu(\text{PCSK9, A}) \neq \mu(\text{PCSK9, P})$

LDL-C, low-density lipoprotein cholesterol; PCSK9, proprotein convertase subtilisin/kexin type-9; P, Placebo; A, AZD8233

The hypotheses are formalised using $\mu(\text{biomarker, treatment group})$ to denote the mean relative reduction of *biomarker* in treatment group at the end of Week 28. For example, the mean relative reduction in concentrations of LDL-C in plasma for AZD8233 after 28 weeks is denoted with $\mu(\text{LDL-C, A})$ and similarly for placebo with $\mu(\text{LDL-C, P})$.

Endpoints that are not listed in Table 6 are of an exploratory nature, and no adjustment will be made for multiple testing of these endpoints.

9.2 Sample Size Determination

Approximately 530 participants will be enrolled to achieve 376 participants randomly assigned to study intervention. Participants will be randomly assigned at a 1:1 ratio to one of the 2 treatment arms listed below:

- AZD8233 CCI, CCI approximately 188 participants randomly assigned
- Placebo matching dose, CCI, approximately 188 participants randomly assigned

CCI [REDACTED]

CCI [REDACTED]

CCI [REDACTED]

Note: “Enrolled” means a participant’s, or their legally acceptable representative’s, agreement to participate in a clinical study following completion of the informed consent

process. Potential participants who are screened for the purpose of determining eligibility for the study, but are not randomly assigned/assigned in the study, are considered “screen failures”, unless otherwise specified by the protocol.

9.3 Populations for Analyses

For purposes of analysis, the following populations are defined:

Table 7 Populations for Analysis

Population/Analysis set	Description
Enrolled	All participants who sign the ICF
Full Analysis Set (FAS)	All participants who were randomly assigned to study intervention. Data from participants will be analysed according to the treatment to which they were randomly assigned.
Safety analysis set (SAS)	The Safety analysis set consists of all participants who have received at least one dose of investigational product. Erroneously treated participants (eg, those randomised to treatment A but actually given treatment B) are accounted for in the treatment group of the treatment they actually received. A participant who has on one or several occasions received active IMP is classified as active and is accounted for the active IMP treatment group.
PK Analysis Set	The PK analysis set will consist of all subjects who receive at least 1 dose of AZD8233, for whom at least 1 post-dose PK concentration assessment is available as determined at the final protocol deviations meeting prior to unblinding of this study. Subjects will be presented in accordance to the actual treatment received.

9.4 Statistical Analyses

The statistical analysis plan will be finalised prior to unblinding and it will include a more technical and detailed description of the statistical analyses described in this section. This section is a summary of the planned statistical analyses of the most important endpoints including primary and secondary endpoints.

9.4.1 General Considerations

Handling of multiple methods for measuring LDL-C

The LDL-C value obtained using PUC will be used in the analysis of LDL-C through reflex testing when the LDL-C is < 40 mg/dL (by the Friedewald method) or if the triglycerides are ≥400 mg/dL. If there is no measurement taken using PUC, the calculated LDL-C value obtained using the Friedewald formula will be used (CCI [REDACTED]). If neither LDL-C measured with PUC or calculated using the Friedewald formula is available, the measurement will be considered as missing. Further details or any additional measurement methods will be described in the SAP.

Baseline

For analyses based on the SAS, the baseline value is defined as the last non-missing value prior to or on the date of administration of the first dose of IMP. For analyses based on the FAS, the baseline value is defined as the last non-missing value prior to or on the date of randomisation. Details are described in the SAP.

9.4.2 Efficacy

9.4.2.1 Primary Endpoint(s)

The primary efficacy variable of relative change in LDL-C from baseline to the end of CCI (visit 16) will be assessed through an estimand which is defined by the following attributes:

- Population: FAS, defined through inclusion and exclusion criteria
- Treatment: AZD8233 CCI or placebo injected CCI on a background of a stable dose of maximally tolerated statin and/or ezetimibe treatment
- Intercurrent events: Non-terminal intercurrent events will be handled using a treatment policy strategy, i.e. the variable of interest is aimed to be collected and used irrespective of intercurrent events. Terminal events are expected to be few without substantial impact on the efficacy estimates and handled in the framework for missing data.
- Population-level summary: difference in variable means between treatments

This estimand requires that to the extent possible, randomised participants are followed up regardless of study intervention compliance.

The main estimator is an ANCOVA for the relative change from baseline to the end of CCI, including all participants in the FAS. The model will include treatment group as a fixed categorical factor and baseline value as a continuous covariate. Additional covariates may be added to the model if deemed necessary, but will be prespecified in the SAP. In this model, the dependent variable will be the relative change in endpoint from baseline to the end of CCI, that is:

$$\frac{(y_{w28} - y_{BL})}{y_{BL}},$$

where y_{w28} and y_{BL} are the measurements of LDL-C at the end of CCI and baseline (BL), respectively.

Available observations at baseline and the end of CCI will be used in the model. Missing observations will be imputed. Any missing baseline values will be imputed based on existing values, disregarding the treatment group. For post-baseline missing values, a distinction in the imputation will be made between non-monotone and monotone missing data. Monotone missing data are defined as missing data which constitute the end of patient follow-up, while non-monotone missing data means that there are observations made after the missing time

point.

Any non-monotone missing data will be replaced using the procedure, PROC MI in the SAS Software, with the Markov Chain Monte Carlo method. The imputation model will include timepoint, baseline value and treatment group.

For monotone missing data, pattern mixture models will be used, assuming missing data are not missing at random. Imputation of monotone missing data will be done separately for each treatment arm.

The preferred method of imputation for monotone missing data will be to use MI-RD for each distinct pattern. Missing data patterns at the end of CCI are defined as:

- Missing data without discontinuation of treatment (including deaths as discontinuation of treatment) prior to the end of CCI
- Missing data after discontinued treatment prior to the end of CCI

For both of these missing data patterns, monotone missing values will be imputed sequentially by visit; for pattern a) based on completers (ie, had follow-up until the end of CCI) in the same treatment arm who had not discontinued treatment, and for pattern b) based on completers in the same treatment arm who had discontinued treatment. The baseline value will be included in the imputation models and data up to each missing visit will be accounted for. This MI-RD approach will be used as long as the number of retrieved dropouts for each combination of treatment arm and missing data pattern is sufficient to construct imputation models. The distribution of missing data, number and proportions, according to each missing data pattern will be summarised per treatment arm.

[figure not shown]
The ANCOVA model described above will be used to provide least-squares means, least-squares mean differences and corresponding standard errors for each of the multiple imputed datasets. These results are then pooled according to Rubin's rules in PROC MIANALYZE in SAS to provide the final estimates as well as p-value.

If MI-RD cannot be used due to an insufficient number of retrieved dropouts, missing data at the end of CCI in the placebo arm will be replaced based on participants in the same arm using standard MI and assuming missing at random, including baseline value and observations between baseline and the end of CCI in the imputation model. Missing values in the active treatment arm will be replaced by washout multiple imputation. In washout multiple imputation, the end of CCI data are imputed based on observed values in the placebo group only, including baseline value in the imputation model but not accounting for any observations after baseline.

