7.1 Discontinuation of Study Intervention

An individual participant will not receive further IMP if any of the following occur in the participant in question:

- Participant decision. The participant is free at any time to discontinue IMP treatment, without prejudice to further treatment
- AE precluding further therapy (where the investigator thinks continued treatment may put the patient at undue risk, regardless of whether the AE is thought to be related to IMP)
- Investigator's decision, including but not limited to these examples:
 - Incorrectly randomised patient in whom the inclusion/exclusion criteria violation would put the patient at undue risk
 - Severe non-compliance to Clinical Study Protocol
- Pregnancy
- Platelet count $< 75 \times 10^9/L$, confirmed by taking a second measurement ([Appendix F](#))
- Hy's Law defined as 'an increase in AST or ALT $\geq 3 \times ULN$ together with TBL $\geq 2 \times ULN$, where no other reason, other than the IMP, can be found to explain the combination of increases', as defined in [Appendix E](#).
- Confirmed:
 - ALT or AST $> 8 \times ULN$
 - ALT or AST $> 5 \times ULN$ for > 2 weeks
 - ALT or AST $> 3 \times ULN$ and TBL $> 2 \times ULN$ or INR > 1.5
 - ALT or AST $> 3 \times ULN$ with the appearance of fatigue, nausea, vomiting, right upper quadrant pain or tenderness, fever, rash, and/or eosinophilia ($> 5\%$).

- Confirmed by repeat testing increase in serum creatinine of 0.3 mg/dL from baseline at the discretion of the investigator
- Confirmed by repeat testing 25% decline in eGFR from baseline at the discretion of the investigator
- Confirmed by repeat testing new onset haematuria of unknown etiology, albuminuria (urine albumin/creatinine ratio [UACR] \geq 300 mg/g), or proteinuria (urine protein/creatinine [UPCR] \geq 500 mg/g) at the discretion of the investigator
- Anaphylactic reaction or severe hypersensitivity reaction suspected to be related to study intervention.

Follow-up for participants who have discontinued IMP

Participants who are prematurely and permanently discontinued from receiving IMP will be encouraged to continue their study participation by following the original visit schedule, without taking IMP, with the exception of the safety monitoring visits during the treatment period.

If the participant is unwilling to comply with the visit schedule, a modified follow-up schedule can be offered, which should at a minimum include the following visits:

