Safety Monitoring Visits (Visits 5, 7, 9, 11, 13, 15): At safety visits, concomitant medications, AEs and an assessment for ISRs will be reviewed. Platelet count and liver function tests will be obtained. A PK sample will be obtained on Visit 15. Participants do not have to be fasting for this visit. Where applicable, the safety monitoring visit may be performed via home visits.

End of Planned Treatment Period Visit (Visit 16): At the end of treatment visit, the participants are required to be fasting for at least 8 hours overnight prior to the visit. Concomitant medications, AEs and an assessment for ISRs will be reviewed. An abbreviated physical exam, a neurologic examination and assessment of vital signs will be performed. Blood samples, including those needed for efficacy and pharmacodynamics, PK and ADA, as well as urine samples, will be collected. Coagulation parameters will also be assessed.

Safety Follow-up Visits (Visit 17, 18): At the safety follow-up visits, participants are required to be fasting for at least 8 hours overnight prior to Visit 18 (not necessary for Visit 17). Concomitant medications and AEs will be reviewed. An abbreviated physical examination and assessment of vital signs will be performed on Visit 17 and a complete

physical examination, a neurologic examination and assessment of vital signs on Visit 18. Additionally, ECG will be obtained. Blood and urine samples, including ADA, will be collected in accordance with the SoA. For participants who have prematurely discontinued IMP, these visits will be adjusted to occur 8 and 16 weeks after the last dose of IMP, as described in Section 7.1.

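### Read literally, a missing Week 28 LDL-C or PCSK9 value that is followed by a Visit 18 sample is imputed without regard to treatment discontinuation, which can modestly favour active

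*Protocol*

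**What the plan says.** Section 9.4.2.1 sets a treatment-policy estimand for relative change in LDL-C at Visit 16, under which "the variable of interest is aimed to be collected and used irrespective of intercurrent events". The label of the time point is blacked out there, but the formula's subscript and Sections 3, 8.1 and 9.1 identify it as Week 28.

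Post-baseline missing values are split in two.

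- **Monotone:** "Monotone missing data are defined as missing data which constitute the end of patient follow-up". These are treated as not missing at random and imputed by arm within two patterns. Pattern (a) covers participants who had not discontinued treatment. Pattern (b) covers those who had: "for pattern b) based on completers in the same treatment arm who had discontinued treatment". If there are too few retrieved dropouts, active-arm values are imputed by washout from placebo.
- **Non-monotone:** "non-monotone missing data means that there are observations made after the missing time" point. These are filled by MCMC, and "The imputation model will include timepoint, baseline value and treatment group".

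The Schedule of Activities (Table 1) draws LDL-C and PCSK9 at Visit 16 (D197) and again at Visit 18 (D281). Under Section 7.1, participants who stop the study drug "will be encouraged to continue their study participation by following the original visit schedule". If unwilling, they may be offered a reduced schedule that keeps Visit 16 and moves the Visit 18 procedures to 16 weeks after the last dose. Section 9.4.2.2 carries the primary analysis method over to PCSK9.

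**The concern.** The plan intends missing values after discontinuation to resemble those of other discontinuers in the same arm or, failing that, placebo. The gate into that route is the definition of monotone missingness, which refers to the end of follow-up and not to the end of the treatment period. Follow-up runs 12 weeks past the endpoint, and a lipid sample is taken at its end.

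One off-drug sample after Week 28 can therefore move a participant out of the discontinuer model. The model that replaces it is informed mostly by people still on treatment and has no listed term for having stopped. In the active arm the likely error is too large an imputed reduction. Placebo participants who stop have no drug effect to lose, so the errors would not be expected to cancel between arms. The point estimates for LDL-C and PCSK9 are at stake, not the conclusion of the tests.

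**Working it through.** The plan gives no figure for this point. The sample-size rationale in Section 9.2 is redacted; 2 × 188 = 376 agrees with its arm sizes, and 188 is the denominator used below.

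**Step 1. Classification.** Visit 16 missing, Visit 18 observed: an observation exists after the missing time point, so the value is non-monotone. It does not close the participant's follow-up, so it is not monotone. Patterns (a) and (b) and the washout fallback are described under the monotone route. No sentence sends a non-monotone Week 28 value back to them.

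**Step 2. When Visit 18 is later than Visit 16 (D197).** On the original schedule Visit 18 is at D281, and 281 − 197 = 84 days, so it is always later. On the reduced schedule it is at last dose + 112 days:

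| Last dose | Visit 18 | After D197 by date? |
|---|---|---|
| D1 | D113 | no |
| D29 | D141 | no |
| D57 | D169 | no |
| D85 | D197 | no (same target day) |
| D113 | D225 | yes |
| D141 | D253 | yes |

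For last doses up to D85 on the reduced schedule, Visit 18 is later only by visit number. The text does not say which ordering governs.

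**Step 3. What such a participant would be given.** The on-treatment mean of −70% is the goal in Section 4.3. The rest is assumed: full effect until 28 days after the last dose, then halving every 28, 56 or 84 days; earlier means of −55% at D29 and −67% at D57; between-person SD 12 points and within-person SD 10. Imputation parameters are those of on-treatment active participants.

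Assumed true Week 28 mean = −70 × 0.5^((197 − last dose − 28)/half-time). For last dose D113 and half-time 28 this is −70 × 0.5^(56/28) = −17.5.

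- *Listed terms only.* The imputed mean is about −70% for everyone.
- *Own values also used, all dosing visits attended, Visit 18 at D281.* Simulated imputed means:

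| Half-time (days) | Last dose | True % | Imputed % | Gap (points) |
|---|---|---|---|---|
| 28 | D29 | −2.2 | −41.0 | 38.8 |
| 28 | D85 | −8.8 | −57.3 | 48.5 |
| 28 | D113 | −17.5 | −64.4 | 46.9 |
| 28 | D141 | −35.0 | −69.3 | 34.3 |
| 56 | D29 | −12.4 | −48.2 | 35.8 |
| 56 | D85 | −24.7 | −60.8 | 36.1 |
| 56 | D113 | −35.0 | −65.6 | 30.6 |
| 56 | D141 | −49.5 | −69.1 | 19.6 |
| 84 | D29 | −22.0 | −51.5 | 29.5 |
| 84 | D85 | −35.0 | −62.3 | 27.3 |
| 84 | D113 | −44.1 | −66.3 | 22.2 |
| 84 | D141 | −55.6 | −69.0 | 13.4 |

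- *Own values used, reduced schedule, last dose D113 or D141.* The imputed mean is about −70%. Visit 18 is then 112 days after the last dose, as it is for completers (169 + 112 = 281), so it carries little sign of having stopped.

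The imputed reduction exceeds the true one in every case. A participant's own off-drug values pull it back clearly only for early stoppers who kept attending.

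**Step 4. Effect on the arm mean.** Shift = k × gap / 188 for k affected participants. Taking gaps of 20 to 40 points, within the range above, and an assumed k of 3 to 8:

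- 3 × 20 / 188 = 0.32 points
- 8 × 40 / 188 = 1.70 points

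**The case against.** The strongest reply is that Section 9.4.2.1 has a Week 28 horizon throughout. Its missing-data patterns are defined at the primary time point, completers are those followed up to that time point, and the placebo fallback model uses observations only up to it. No sentence places Visit 18 in the imputation dataset. Section 9.4 also calls the text a summary and leaves technical detail to the SAP. This makes a Visit 16 cut-off a possible intention, and a reader should not infer that the sponsor will certainly use Visit 18 in this way. But those phrases lie inside the monotone route, and the definition that decides entry to it does not state the limit. The protocol has fixed both the definition and the model terms, so this is wording to correct and not detail left for later.

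The second reply is that the affected group is narrow: on active, stopped, Visit 16 missed, Visit 18 attended, although Visit 16 is retained even on the reduced schedule. This stands. Section 4.1 aims for at least 150 of about 188 active participants completing treatment, which leaves up to 38. Eight affected would be 8/38 = 21% of them, and nothing in the protocol supports a share that high.

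Third, a reader might infer that the model has exactly three terms and so always returns about −70%. The text does not settle this. Listing timepoint may mean that LDL-C values at other visits enter, in which case early stoppers who attended the dosing visits are drawn part of the way back. The error shrinks but does not vanish.

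**Conclusion.** The point holds as a defect of wording with a modest, conditional consequence. By its literal definition, the plan sends some discontinuers' missing Week 28 values to a model that lists no discontinuation status, against its own treatment-policy aim and its not-missing-at-random handling of discontinuers. The likely direction favours active.

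The size is about 0.3 to 1.7 points on the active-arm mean, and the lower part of that range is the more plausible. Recovery rate, SDs, per-person error and number affected are all assumptions; the documents give none of them.

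A reader might go further and conclude that the plan overstates efficacy or that the primary test is unsafe. The documents do not support either. Whether anyone falls into this group is unknown, and a shift of this size is small beside a targeted 70% reduction, so no change to the primary test is expected. The correction is still worth making because it costs almost nothing and removes an ambiguity in the primary and secondary analyses.

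**What to change.** State in Section 9.4.2.1, and repeat in the SAP, that monotone versus non-monotone missingness is judged only on visits up to and including Visit 16. Every missing Week 28 value is then handled under pattern (a) or (b), or the stated fallback, by discontinuation status, whether or not a Visit 18 sample exists. Keep the MCMC step for gaps before Week 28.

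The cost is one sentence; discontinuation status is already needed to form patterns (a) and (b). The small downside is that the Visit 18 value no longer helps predict Week 28. Adding on/off-treatment status to the MCMC model for earlier gaps is optional and not part of the error.
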